Following successful completion of Phase 1, we will proceed with Phase 2 of the study. The aims of this phase will be:

- 1. Assess the sensitivity and specificity of a panel of DNA methylation markers in the nonendoscopic detection of BE using a capsule sponge device.
- 2. Assess the sensitivity and specificity of a panel of DNA methylation markers in the nonendoscopic detection of BE related dysplasia/carcinoma using a capsule sponge device.
- 3. Estimate the degree of missed dysplasia during routine surveillance endoscopy with random endoscopic biopsies, by utilizing follow up intensive endoscopic surveillance and capsule sponge examination.
- 4. Explore the utility of demographic, anthropometric and circulating biomarker risk factors in predicting the presence of BE and BE related dysplasia.

The inclusion and exclusion criteria, study procedures and biomarker assays will be identical to those described in Phase 1. All subjects will undergo the capsule sponge assessment followed by the clinically indicated endoscopy as described in Phase 1. All studies will be conducted using a single size sponge with the same porosity configuration selected from Phase 1. Study procedures, testing and follow up will be similar to that in Phase 1. Recruitment will be monitored and a future interim analysis may be conducted.

In addition to Mayo Clinic Rochester, subjects will also be recruited at Mayo Clinic Jacksonville; Mayo Clinic Arizona; Mayo Clinic Health Systems – Austin; Mayo Clinic Health Systems – Mankato; Northwell Health in Manhasset, NY; and Baylor University Medical Center in Dallas, TX. Enrollment is closed at University of Colorado, Denver – Anschutz Medical Campus in Aurora, CO.

[name] will be site PI at Mayo Clinic Jacksonville. [name] will be site PI at Mayo Clinic Arizona. [name], MD will be the site PI at Mayo Clinic Health Systems – Austin. [name] will be the site PI at Mayo Clinic Health Systems – Mankato. [name] will be site PI at Northwell Health. [name] will be the site PI at Baylor University Medical Center.

Preliminary Data:

Identification and initial feasibility testing of methylated DNA markers for BE diagnosis.

We aimed to prospectively assess the accuracy of methylated BMP3 and NDRG4 to identify BE using endoscopic biopsies (Phase 1) and brushings from the whole esophagus and cardia to simulate non-endoscopic sampling devices (Phase 2).

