Methods: Cases with and controls without BE were recruited prior to endoscopy. BE cases had >1cm of circumferential columnar mucosa with confirmed intestinal metaplasia; controls had no BE endoscopically. In Phase 1, biopsies were obtained in cases from BE, gastric cardia ((GC); 1

cm below Z-line) and squamous epithelium ((SE); >2 cm above BE) and in controls from GC (as for BE) and SE (5 cm above Z-line); then promptly frozen. Biopsy samples were processed as a batch, and assayed in blinded fashion. In Phase 2, specimens were obtained using a high capacity endoscopic cytology brush (Hobbs Medical, Stafford Springs CT); the cardia, BE (in cases), and full esophageal length were brushed to simulate a swallowed sponge sampling device. Following DNA extraction and bisulfite treatment, methylation on target genes was assayed by quantitative allele-specific real-time target and signal amplification. β -actin was also quantified as a marker for total human DNA.

Results: We prospectively studied 100 subjects. Phase 1: Among 40 BE cases and 40 controls: median age was 65 (quartiles 55-77) and 54 (37-69) and men comprised 78% and 48%, respectively. Median BE length was 6 cm (range 3-10). Median levels of methylated markers were substantially higher (34-600 times) in BE than in adjacent SE and GC or than in normal SE and GC (Table 1). In contrast to methylated markers, β -actin distributions were similar across tissue groups. Both marker levels increased with BE length and age, p<0.001 whereas only NDRG4 increased significantly with presence of dysplasia (none (19), low grade (9), high grade (11); p=0.003). Factors not significantly affecting marker levels included sex and inflammation. Phase 2: Among 10 BE cases and 10 controls, median age was 64 (59-70) and 66 (49, 71) and men comprised 80 and 30% respectively. Median BE length was 2 cm (range 1-4). Discrimination of BE by markers was extraordinary with AUC of 1.0 for NDRG4 and 0.99 for BMP3; levels were >100 times higher in cases than controls (Figure 1).

[figure not shown]
Conclusions: Selected methylated DNA markers highly discriminate BE from normal GC and SE, both in biopsy and brushed specimens, and hold promise for non-endoscopic screening applications.

Table 1: Marker levels (copy numbers of markers adjusted for beta actin) for BMP3 and NDRG4 biopsies from BE cases (cardia, Barrett's, squamous) and controls (cardia, squamous).

	BM	1P3	NDRG4			
	Normal	Barrett's	Normal	Barrett's		

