Participants: Patients with and without known BE will be recruited from the Esophageal, Barrett's esophagus and general gastroenterology clinics in Mayo Clinic, Rochester (Phase I and 2), Mayo Clinic Health Systems – Austin, Mayo Clinic Health Systems – Mankato, Mayo Clinic Florida, Mayo Clinic Arizona, Northwell Health, and Baylor University Medical Center,. (Phase 2 only). Patients with known BE will be recruited to enrich the sample with BE subjects and those with BE related dysplasia/carcinoma. Potential cases declining to participate in the capsule sponge procedure or those not eligible due to exclusion criteria b.3. below will have the option to participate in the esophageal brushings portion of the study.

Inclusion criteria:

- a. Subjects with known BE.
 - 1. Patient between the ages 18 90.
 - 2. Patients with a BE segment ≥ 1cm in maximal extent endoscopically.
 - 3. Histology showing evidence of intestinal metaplasia with or without presence of dysplasia.
 - 4. Undergoing clinically indicated endoscopy.
- b. Subjects without known evidence of BE
 - 1. Undergoing clinically indicated diagnostic endoscopy.

Exclusion criteria:

- a. Subjects with known BE.
 - 1. Patients with prior history of ablation (photodynamic therapy, radiofrequency ablation, cryotherapy, argon plasma coagulation). *Patients with history of endoscopic mucosal resection alone will not be excluded.*
 - 2. Patients with history of esophageal resection for esophageal carcinoma.
- b. Subjects with or without known evidence of BE (on history or review of medical records).
 - 1. Pregnant or lactating females.
 - 2. Patients who are unable to consent.
 - 3. Patients with current history of uninvestigated dysphagia (this does not apply to the brushings only portion of the study).
 - 4. History of eosinophilic esophagitis, achalasia.
 - 5. Patients on oral anticoagulation including Coumadin, Warfarin.

- 6. Patients on antiplatelet agents including Clopidogrel, unless discontinued for at least three days prior to the sponge procedure.
- 7. Patients on oral thrombin inhibitors including Dabigatran and oral factor X a inhibitors such as rivaroxaban, apixaban and edoxaban, unless discontinued for at least three days prior to the sponge procedure.
- 8. Patients with history of known varices or cirrhosis.
- 9. Patients with history of esophageal resection for esophageal carcinoma.
- 10. Patients with congenital or acquired bleeding diatheses.

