In addition, clinically archived FFPE tissue from up to 10 cases will be used to assess methylated DNA marker levels in biopsies versus the sponge.

Due to the known dysplasia miss rate with routine surveillance endoscopy, we hypothesize that there will be undetected or missed dysplasia in BE patients with a negative surveillance histology. This imperfection in the endoscopic "gold" standard will bias the resulting accuracy estimates of methylation markers in a multitude of ways. There are several approaches in the literature to address this issue; all with their own caveats. The three approaches that will be investigated are latent class analysis, Bayesian estimation, and discrepant resolution. We have hence inflated the sample size estimates in table 2 to correspond with a 30% prevalence of undetected dysplasia in those with no dysplasia on conventional surveillance endoscopy to ensure that we have 50 true BE subjects without dysplasia.

Table 2

	BE vs. No BE			BE no dysplasia vs. BE w/dysplasia				
Confidence Level	0.95	0.95	0.95	0.95	0.95	0.95	0.95	0.95
Sensitivity	0.75	0.80	0.85	0.90	0.75	0.80	0.85	0.90
Confidence bands	0.085	0.078	0.070	0.059	0.105	0.097	0.087	0.073
N no BE/BE without dys/BE with dys	100	100	100	100	65	65	65	65

Statistical analysis

Phase 1: Tolerability score and level of mucosal abrasion will be summarized as median and interquartile range. Analysis of variance will be used to detect statistically significant differences in tolerability score and level of mucosal abrasion between different levels of sponge porosity and size. Failure/complication rate will be summarized as the percentage of the group total. Comparisons between sponge porosity and size for failure/complication rate will be analyzed using the Chi-squared test.

Phase 1 and 2: Marker specificity will be defined as the 90th percentile value in subjects without BE. Several markers will be combined based on the coefficients from a logistic regression model using subjects with BE vs subjects without BE as the response. This approach is used as they represent the broadest spectrum of disease and any marker combination that fails to discriminate between these two subgroups would not be of future value. The specificity of the combined markers will then be set equal to the 90th percentile in non-BE subjects. The corresponding sensitivity of individual markers as well as combined markers will be estimated with 95% confidence intervals.

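### Aim 1 reads BE sensitivity from one pooled case group enriched with dysplasia and carcinoma, so the figure may overstate sensitivity for non-dysplastic BE; add stratum estimates at the same cut-off

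*Combined protocol and SAP*

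**What the plan says.** All references are to the combined protocol and SAP.

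- **Aim.** Phase 2 Aim 1 is to "Assess the sensitivity and specificity of a panel of DNA methylation markers in the nonendoscopic detection of BE using a capsule sponge device". It names no dysplasia stratum.
- **Recruitment.** Under Participants, "Patients with known BE will be recruited to enrich the sample with BE subjects and those with BE related dysplasia/carcinoma". The inclusion criteria for known BE accept "Histology showing evidence of intestinal metaplasia with or without presence of dysplasia". No proportion with dysplasia is fixed or capped.
- **Aim 1 analysis.** Under Statistical analysis, Phase 1 and 2, markers are combined through a "logistic regression model using subjects with BE vs subjects without BE as the response". Then "The specificity of the combined markers will then be set equal to the 90th percentile in non-BE subjects", and sensitivity is estimated with a 95% interval. The stated reason for this contrast is that it covers the widest range of disease.
- **Dysplasia analysis.** The paragraph that follows uses BE without dysplasia as the control group, with a separate cut-off taken from that group.
- **Sample size.** Table 2 gives 100 in the BE vs no BE columns and 65 in the dysplasia columns, on a row labelled "N no BE/BE without dys/BE with dys".
- **Preliminary data.** In the biopsy study both BMP3 and NDRG4 rose with BE length and age (p<0.001), whereas "only NDRG4 increased significantly with presence of dysplasia" (p=0.003).

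**The concern.** The documents motivate the device as a non-endoscopic way to find BE, and finding BE without dysplasia is a large part of that task. A pooled sensitivity is a weighted average over case types. Here the weights come from whom the sites recruit, not from a defined population. If dysplastic cases carry higher marker levels, more of them pass a cut-off fixed in subjects without BE, and the average rises with their share.

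The dysplasia analysis does not fill the gap. Non-dysplastic BE appears there only as the control group at a different cut-off, so no planned analysis gives its sensitivity against no BE. A reader could take the pooled figure as applying to non-dysplastic BE and would have nothing in the report to check it against. Table 2's intervals cover sampling error only and say nothing about case mix.

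**Working it through.** **1. The plan's own figures.** Wald half-width = 1.96 × √(p(1−p)/n).

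| Sensitivity | n=100 | Table 2 | n=65 | Table 2 |
|---|---|---|---|---|
| 0.75 | 0.0849 | 0.085 | 0.1053 | 0.105 |
| 0.80 | 0.0784 | 0.078 | 0.0972 | 0.097 |
| 0.85 | 0.0700 | 0.070 | 0.0868 | 0.087 |
| 0.90 | 0.0588 | 0.059 | 0.0729 | 0.073 |

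All eight entries reproduce.

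**2. Effect of case mix.** Let w be the dysplasia/carcinoma share among BE cases.

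Pooled = w × S_dys + (1 − w) × S_nondys, so pooled − S_nondys = w × (S_dys − S_nondys).

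The documents give neither w nor the gap, so both are assumed below. A 50% share is what 65/(65+65) gives if the dysplasia columns of Table 2 mean 65 per group. The 25% share is an alternative for range.

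| Assumed gap (points) | Overstatement, w=25% | Overstatement, w=50% |
|---|---|---|
| 0 | 0 | 0 |
| 10 | 2.5 | 5 |
| 15 | 3.75 | 7.5 |
| 20 | 5 | 10 |

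Example: S_nondys = 75% and S_dys = 90%. At w=50%, pooled = 0.5 × 90 + 0.5 × 75 = 82.5%. At w=25%, pooled = 0.25 × 90 + 0.75 × 75 = 78.75%.

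The gap cannot exceed 100% minus S_nondys. At S_nondys = 90% it is at most 10 points, so the overstatement is at most 5 points at w=50%.

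**3. Comparison with precision.** Table 2's half-widths for this endpoint are 5.9 to 8.5 points at n=100. If the pooled group were 130, they would be 5.2 to 7.4. At w=25% every value in the table above is below 5.2. At w=50% a 10-point gap also stays just below 5.2, while gaps of 15 to 20 points reach or pass the half-widths.

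**4. Evidence that the gap may be small.** In the marker-level table of the Preliminary Data (composite rows), the 90th percentile in controls is 10.0 for BMP3 and 8.1 for NDRG4. The lower quartile in BE cases is 67.1 and 68.9, which is 67.1/10.0 = 6.7 and 68.9/8.1 = 8.5 times higher. Of the 39 cases listed by dysplasia status (19 none, 9 low grade, 11 high grade), 19 had none. In brushings the AUC was 1.0 for NDRG4 and 0.99 for BMP3, with a median BE length of 2 cm.

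These data have limits. The table is not split by dysplasia status. The biopsy cases had long segments (median 6 cm). The brushing study had 10 cases and 10 controls with no dysplasia mix reported. Neither used sponge samples, and Table 2 itself plans for sensitivities of 0.75 to 0.90, where there is room for a gap.

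**5. Precision in a stratum.** With 65 non-dysplastic cases the half-widths are 10.5, 9.7, 8.7 and 7.3 points at sensitivity 0.75, 0.80, 0.85 and 0.90. At 0.75, a half-width of 8.5 points needs 1.96² × 0.1875 / 0.085² ≈ 100 non-dysplastic cases.

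**6. Hidden dysplasia.** The plan assumes 30% undetected dysplasia among histology-negative BE. In a stratum of 65 that is 0.30 × 65 = 19.5 subjects. If hidden and detected dysplasia had the same sensitivity, the stratum estimate would still be high by 0.30 × gap: 3 points for a 10-point gap and 6 for a 20-point gap.

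**The case against.** The pooling is open and reasoned. Aim 1 targets BE, the inclusion criteria admit BE of any dysplasia status, a rationale is given, and the plan describes itself as an early feasibility study. This stands: there is no contradiction in the plan, and choosing non-dysplastic BE as the headline would be a different estimand, not a correction.

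A reader might infer that the plan sets a 50:50 quota and that the pooled figure therefore overstates sensitivity by 5 to 10 points. The documents do not support that. The equal split is inferred from the dysplasia columns of Table 2, whose row label is ambiguous, while the BE columns show 100. The sample-size text also asks for 140 to 210 cases with no mix stated and allows up to 1000 participants. Subjects without known BE can be diagnosed at the study endoscopy, which shifts the share again. The gap is unknown and may be zero.

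A reader might also infer that the Aim 1 coefficients will reward dysplasia markers. The evidence is mixed. BMP3 did not rise significantly with dysplasia in the biopsy study. The Biomarker assays section names BMP3, NDRG4, TFPI2 and HPP1 for their levels in BE relative to squamous mucosa and treats the dysplasia markers separately. On the other hand, BMP3 and NDRG4 are both among the 12 markers selected for separating dysplastic from non-dysplastic BE, and the plan does not say which of its 14 or more markers enter which model.

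What the objection does not answer is the missing estimate. The stated rationale is a reason for building the panel on this contrast, not for reporting a single sensitivity from a mix set by recruitment.

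**Conclusion.** The concern holds as a gap in reporting. The plan enriches the BE group with dysplasia and carcinoma, pools it for Aim 1, and never estimates sensitivity for non-dysplastic BE against no BE. The plan's own data on NDRG4 and on BE length make an upward shift plausible, so the pooled figure may overstate that sensitivity.

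The size is 0 to 10 points under an assumed share of 25% to 50% and an assumed gap of 0 to 20 points. It is comparable with the Table 2 half-widths only towards the upper end of that range, and it may be near zero if non-dysplastic cases also lie well above the cut-off. The documents cannot settle which applies. This is an inexpensive improvement to the analysis text, not a flaw that invalidates Aim 1.

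**What to change.** In Statistical analysis, Phase 1 and 2, keep the pooled logistic fit and the cut-off from subjects without BE, and add:

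- sensitivity with a 95% interval at that same cut-off, separately for histologically non-dysplastic BE and for BE with dysplasia/carcinoma;
- the same by BE segment length, in prespecified categories;
- the all-BE sensitivity reported only alongside these, with its dysplasia share stated;
- a sentence saying that, under the assumed 30% undetected dysplasia, the histology-negative stratum remains partly contaminated.

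Refitting the panel on non-dysplastic BE vs no BE should be a sensitivity analysis at most. With 65 such cases and 14 markers there would be 65/14 ≈ 4.6 events per marker, against the plan's own rule of 10 to 15.

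**Cost.** No new data are needed, since histology and the endoscopic landmarks are already recorded. Stratum intervals are wider: about ±10.5 points at sensitivity 0.75 if n=65. The text should say that the stated precision of less than ±9% applies to the pooled figure only.

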Screening for BE is currently performed using conventional sedated endoscopy (sEGD) which reveals the replacement of the normal squamous lining of the esophagus by metaplastic columnar epithelium in subjects with BE. However sedated endoscopy is expensive with both direct and indirect costs and not suitable for widespread application. It is also associated with potential complications.(10) Other techniques such as unsedated transnasal endoscopy (uTNE) have comparable accuracy to sEGD with lower cost, but continue to be poorly regarded as a widely applicable tool by providers.(11-13) Despite adequate access to the uTNE device the utilization of uTNE by referring physicians remains limited.(14) The absence of accurate risk stratification tools to determine BE risk and target screening efforts are additional limitations to a widely applicable BE screening.(10)

Endoscopic detection of dysplasia is currently performed using four quadrant random biopsies every 1-2 cm of the BE segment in addition to careful inspection of the BE segment with high resolution white light imaging and advanced imaging techniques. While this has been

recommended by GI societies (3-5), the compliance with these recommendations amongst practicing gastroenterologists remains poor.(15) Indeed compliance decreases with increasing BE segment length leading to increasing rates of missed dysplasia. Other challenges with dysplasia detection in BE include the spotty distribution of dysplasia in BE(16) which leads to sampling error, poor inter-observer agreement amongst pathologists while grading dysplasia and the relatively poor sensitivity of current surveillance strategies in detecting prevalent dysplasia or carcinoma.(17) The utility of advanced imaging techniques in the community remains unclear with only a third of practicing gastroenterologists reporting use routinely in BE surveillance.(18)

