- 11. Patients with a history of esophageal squamous dysplasia.
- 12. Patient has known carcinoma of the foregut (pancreatic, bile duct, ampullary, stomach, or duodenum) within 5 years prior to study enrollment.

Study procedures:

Participants will report fasting for ≥ 6 hours for the study.

A. Pre-procedure assessment:

- a. Baseline height, weight, hip, and waist circumference will be measured by the research coordinator.
- A validated questionnaire assessing reflux symptoms (RSQ) will be completed by the subject.
- c. At the Mayo Clinic sites only, 10 ml of blood will be obtained via venipuncture for measurement of circulating biomarkers (cytokines, adipokines and methylated DNA markers) of BE risk. Blood will be processed and separated into serum, plasma, and buffy coat for subsequent analysis for BE biomarkers.

Figure 1:25 mm sponge, intact and expanded

- d. Pregnancy test will be obtained for women of child bearing potential.
- B. Capsule sponge assessment:

For phase 1 subjects will be randomized using concealed allocation to one of two capsule sponges: 25 mm 10 ppi, 25 mm 20 ppi. All phase 2 subjects will receive the same single size and porosity sponge (porosity to be determined after analysis of Phase 1).

 Participants will be seated upright and asked to swallow the capsule sponge to which they have been randomized to, with

Figure 2: 30 mm sponge, intact and expanded

sips of water. The pharynx will then be anesthetized with Benzocaine 20% aerosol

- spray (Topex). After an interval of 5-10 min, the capsule sponge will be pulled out using steady traction using the string attached to the capsule sponge. As detailed in another Mayo IRB approved protocol (IRB 11-006429). The sponge will then be placed in a preservative solution and transferred to the laboratory for storage and subsequent analysis.
- b. Following completion of the capsule sponge study participants will fill out a tolerability questionnaire which allows patients to grade of discomfort during the procedure on a Likert scale of 0-10. 10 representing the "worst experience" and 0 the "best experience." This scale allows a comprehensive and individual assessment of the degree of pain, choking, gagging, and anxiety experienced during the procedure. Participants will also be asked if they would have the procedure again (yes/no).

C. Endoscopic assessment:

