- a. All participants will undergo a diagnostic clinically indicated sedated endoscopy within 24 hours of the Capsule sponge test. This will be performed in one of the clinical endoscopy units at Mayo Clinic Rochester, Mayo Clinic Florida, Mayo Clinic Arizona, Mayo Clinic Health Systems – Austin, Mayo Clinic Health Systems - Mankato, Northwell Health, and Baylor University Medical Center.
- b. Patients will receive sedation (using a combination of intravenous midazolam and Demerol) or monitored anesthesia care as clinically appropriate and undergo clinically indicated endoscopy with standard endoscopic equipment.
- i. The following landmarks will be identified, recorded (in centimeters from the incisors) and photographed: squamo-columnar junction, gastroesophageal junction (GEJ) (defined as top of the gastric folds with the esophagus partially deflated) and the diaphragmatic hiatus. Endoscopically suspected BE will be defined as the presence of ≥ 1cm of columnar mucosa above the GEJ. Targeted clinical biopsies will be obtained to confirm a diagnosis of BE. Presence of intestinal metaplasia with goblet cells will be a pre-requisite for the diagnosis of BE (histologically confirmed BE).
- ii. The presence or absence of esophagitis will be recorded. If present, esophagitis will be graded as per the LA classification.
- iii. The presence of any trauma from the passage of the sponge will be assessed and recorded photographically. This will be defined as:
 - 1. No evidence of trauma
 - 2. Superficial mucosal abrasion without bleeding
 - 3. Superficial mucosal tear abrasion with minimal oozing similar to that from biopsy.
 - 4. Deep mucosal abrasion without bleeding.
 - 5. Deep mucosal abrasion with greater than minimal oozing.
 - 6. Bleeding requiring endoscopic therapy.
- iv. In those with known BE, clinical surveillance biopsies (with or without endoscopic mucosal resection if clinically indicated for visible lesions) will be obtained as per current clinical recommendations: four quadrant biopsies every 1-2 cm. All clinical histology will be read by GI pathologists as per standard practice at Mayo Clinic Rochester, Mayo Clinic Florida, Mayo Clinic Arizona, or Mayo Clinic Health Systems. Slides or scanned slides from Northwell Health and Baylor University Medical Center

- will be sent to Mayo Clinic Rochester GI study Pathologist to confirm Barrett's Esophagus and dysplasia grade.

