- v. Endoscopic brushings will be obtained from the Barrett's mucosa in BE cases, and from the squamous mucosa in control subjects. Brushings will be obtained using a high capacity cytology brush (Hobbs Medical) to enable detection of methylation biomarkers of dysplasia. 1 brush will be used for every 5 cm of Barrett's epithelium in BE case subjects. In control subjects, 1 brush will be used to sample the cardia and the distal 5cm of the esophageal squamous mucosa. These brushings will be stored at -80°C for identification of additional biomarkers.
- vi. Two research biopsies will be obtained from the gastroesophageal junction in controls for identification of methylated DNA biomarkers from the GEJ. One will be frozen and stored at -80°C and one will be formalin fixed, paraffin embedded.
- vii. The diagnostic part of the procedure will be video recorded and stored in a deidentified fashion for subsequent review.
- viii. Patients who are biomarker positive (for dysplasia related DNA methylation markers) but negative for dysplasia, as well as those biomarker negative but positive for dysplasia on clinical surveillance histology will be offered a research endoscopy (funded by the study) after biomarker analysis is complete, for additional endoscopic surveillance to detect prevalent dysplasia which may have been missed at the initial study endoscopy as well as assess for sensitivity of the marker panel. In addition to surveillance biopsies (paid for by the study), sponge procedure will be repeated and research esophageal brushings using a high capacity endoscopic brush (Hobbs Medical) will be obtained for detection of methylated biomarkers of dysplasia.
- ix. An equal number of biomarker negative (for dysplasia related DNA methylation markers) who are negative for dysplasia on clinical surveillance histology will also be offered a research endoscopy (funded by the study) In addition to surveillance biopsies (paid for by the study), sponge procedure will be repeated, and research esophageal brushings using a high capacity endoscopic brush (Hobbs Medical) will be obtained for detection of methylated DNA biomarkers of dysplasia.

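### No masking is specified for the second-look endoscopist or pathologist, although the second look is offered because of the marker result

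*Combined protocol and SAP*

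**What the plan says.** All references are to the combined protocol and SAP.

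- **Who gets a second look** (Study procedures, C. Endoscopic assessment, item viii). The discordant group is given as "Patients who are biomarker positive (for dysplasia related DNA methylation markers) but negative for dysplasia, as well as those biomarker negative but positive for dysplasia"; dysplasia status here means the routine histology. The second look takes place once the marker results are in, and is "for additional endoscopic surveillance to detect prevalent dysplasia which may have been missed at the initial study endoscopy". The same item gives a further purpose, assessing how sensitive the marker panel is.
- **Comparison group** (item ix). The plan adds a control set: "An equal number of biomarker negative (for dysplasia related DNA methylation markers) who are negative for dysplasia on clinical surveillance histology will also be offered" the same research procedures.
- **Combined visits** (item x): the second visit may be done during a clinically indicated endoscopy that includes, for example, ablation or mucosal resection.
- **Histology** (item iv): "All clinical histology will be read by GI pathologists as per standard practice". A study pathologist confirms slides from two external sites only.
- **Masking** (Biomarker assays, a): both marker sets are quantified blind in the laboratory. No masking is stated for any endoscopist or pathologist.
- **Subjectivity**: the background lists spotty distribution, sampling error and "poor inter-observer agreement amongst pathologists while grading dysplasia" among the problems of dysplasia detection.
- **Use of the readings**: Phase 2 Aim 3 estimates missed dysplasia from follow-up surveillance. Discrepant resolution is one of three approaches to the imperfect reference standard (Sample size and Statistical analysis).
- **Phase 1**: "subjects will be randomized using concealed allocation to one of two capsule sponges" (section B). At endoscopy, "The presence of any trauma from the passage of the sponge will be assessed and recorded photographically" in six grades (C, item iii). Mucosal irritation is one of four criteria for choosing the sponge (Study Design).

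**The concern.** At the second look, the marker result already exists and is the reason for the invitation. Dysplasia is patchy and graded with poor agreement, so an endoscopist who knows the marker is positive may look longer and take more biopsies, and a pathologist may call borderline changes more readily. The reference reading would then depend on the test it is meant to judge.

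The double-negative group is a useful control, but only if it is searched and read in the same way as the marker-positive group. The invitation rule can itself disclose the marker result. Dysplasia-positive patients are invited only when marker-negative, so anyone who knows the index histology can infer their marker status. Index-negative invitees are a mixture of marker-positive and marker-negative patients, so masking is feasible there, but the plan does not use it.

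At stake are the missed-dysplasia estimate and any accuracy figure corrected by discrepant resolution. In Phase 1, concealed allocation protects the assignment but not the later visual grading of trauma.

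**Working it through.** The plan gives no figure for reader bias, so every bias below is an assumption. The nearest planned figure is the power for the abrasion score.

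**Plan's figure.** Difference 1, SD 1, 20 per group, two-sided 5%. The noncentrality is 1/√(2/20) = 3.16, and a two-sample t-test on 38 df gives 86.9% power, against 86% stated. It reproduces, and masking does not change it.

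**Second look: inputs**
- 65 Barrett's patients without dysplasia at the index endoscopy (Table 2).
- 30% of them with undetected dysplasia (text before Table 2).
- Marker sensitivity 0.75, the lowest value in Table 2; specificity 0.90, from the 90th-percentile cut-off.
- Second-look detection d₊ = 0.90 in marker-positives and d₋ = 0.80 to 0.50 in double-negatives. These are assumed; the documents give no detection rates.

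**Step 1, missed cases.** 65 × 0.30 = 19.5. Marker-positive: 19.5 × 0.75 = 14.625. Marker-negative: 4.875.

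**Step 2, apparent marker sensitivity among missed cases**, if all double-negatives are examined or reweighted: 0.75 d₊ / (0.75 d₊ + 0.25 d₋).

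| d₊ | d₋ | Apparent sensitivity |
|---|---|---|
| 0.90 | 0.90 | 0.75 |
| 0.90 | 0.80 | 0.675/0.875 = 0.77 |
| 0.90 | 0.70 | 0.675/0.850 = 0.79 |
| 0.90 | 0.60 | 0.675/0.825 = 0.82 |
| 0.90 | 0.50 | 0.675/0.800 = 0.84 |

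In counts for the 0.60 row: 14.625 × 0.9 = 13.16 and 4.875 × 0.6 = 2.93, so 13.16/16.09 = 0.82.

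**Step 3, the equal-number sampling.** Marker-positive index-negatives number 14.625 + 45.5 × 0.10 = 19.175, which leaves 45.825 double-negatives. If only 19.175 of those are examined, they contain 4.875 × 19.175/45.825 = 2.04 missed cases. With perfect, even-handed detection, the unweighted sensitivity is then 14.625/(14.625 + 2.04) = 0.88. If the equal number is matched to all discordant patients, more double-negatives are examined and the shift is smaller. Either way, the sampling needs its own weighting.

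**Step 4, the overall miss rate** (assumed truth 30%)
- 90% and 60% detection: 16.09/65 = 24.8%.
- Uniform 90%: 17.55/65 = 27.0%.
- Uniform 60%: 11.7/65 = 18.0%.

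Uneven detection gives a rate above one even-handed comparator and below the other. Over-grading could push it up, but is not modelled here.

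**Phase 1.** With no true difference, suppose grading differs systematically between sponges by b points. The chance of a significant t-test has noncentrality b/(SD × √(2/20)). With SD 1, b = 0.25 gives about 12% and b = 0.5 about 34%, instead of 5%. With SD 1.5 (the plan's range/4 rule on a range of 6), these are about 8% and 18%. The shift b is assumed, and its sign is unknown.

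**The case against.** The strongest reply is that the documents are silent. They nowhere say that endoscopists or pathologists receive marker results, or that the trauma grader sees the sponge. That stands: a reader might infer that readings are open, but the supportable statement is that no masking is specified. Silence still matters here, because the plan states blinding where it wants it, for the assays, and makes the marker result the ground for invitation.

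Other replies also hold in part:

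- **Shared procedures.** Double-negatives get the same listed procedures. This is a partial safeguard, but it does not equalise search effort or grading.
- **Main accuracy estimates.** A reader might infer that these are biased. The documents do not support that. The index endoscopy follows the sponge within 24 hours, the sponge is stored for later analysis, and the sensitivity analyses are not described as using second-look readings.
- **Miss rate.** A reader might infer that it is inflated. Step 4 shows that the direction depends on the comparator.
- **Masking as a full cure.** A reader might infer that masking alone would recover 0.75. Step 3 shows that selective sampling distorts the unweighted figure even with perfect reading.
- **Feasibility.** When the second visit is combined with a clinical procedure, the operator can hardly be kept unaware of its indication. Coded slide reading still works.
- **Phase 1.** Some trauma grades have observable anchors, the sponge goes into preservative after withdrawal, and photographs and de-identified video are kept. Nothing shows a preference for either porosity, so a tilt towards one sponge cannot be claimed.

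**Conclusion.** The gap is real and worth closing. As written, the plan allows second-look reference readings to depend on the marker result, in a setting where it concedes sampling error and poor agreement. The likely effect is to favour the marker in Aim 3 and in discrepant resolution.

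The size is illustrative: 0.77 to 0.84 instead of 0.75 for marker sensitivity among missed cases. It rests on assumed detection of 90% in marker-positives and 80% to 50% in double-negatives, and on all double-negatives being examined or reweighted. The change in the overall miss rate cannot be determined from the documents. Phase 1 grading is a secondary point, with no direction of bias claimed.

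**What to change.** Add to the endoscopic assessment section:

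- Second-look slides are read under code by pathologists who know neither the marker result nor the invitation stratum.
- Marker-positive and marker-negative patients who were index-negative are scheduled under one common label, and the endoscopist is not told the marker result.
- Where the second visit is combined with a clinical procedure, or the patient was dysplasia-positive at the index endoscopy, rely on coded slide reading and record that the endoscopist was not masked.

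For Phase 1, state that the endoscopist grading trauma is not told the sponge porosity, or that grading is done from the planned photographs without knowledge of porosity.

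The cost is minor coordination by the study team. No extra readers, procedures or patients are needed. Weighting for the equal-number sampling is a separate analysis matter that masking does not replace.
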